### **7.7. Study Drug Overdose Management**

The medical monitor must be contacted in the event of any study drug overdose.

An overdose is defined as a known deliberate or accidental administration of study drug, to or by a study patient, at a dose above that assigned to that individual patient according to the study protocol.

For this study, any dose of relugolix > 80 mg within a 24-hour window is an overdose and any dose of estradiol/norethindrone acetate > 2 x the protocol dose is an overdose (ie, more than 2 capsules taken within a 24-hour window). There is no known antidote for an overdose.

In the event of an overdose, the investigator or treating physician should:

- Contact the medical monitor immediately;
- Closely monitor the patient for adverse events and laboratory abnormalities;
- All overdose events are to be reported within 24 hours of awareness by the study site, using a serious adverse event form according to Section 7.6, whether or not the overdose is associated with an adverse event;
- Document the quantity of the excess dose as well as the duration of the overdosing in the eCRF.

The medical monitor, in consultation with the investigator, will make decisions regarding patient status and potential dose interruptions, based on the clinical evaluation of the patient.

### **7.8. Pregnancy Reporting**

If any patient becomes pregnant during the study, the site must discontinue the patient from the study treatment immediately and have her return for an Early Termination visit.

If the patient agrees, the investigator should notify the patient's primary care physician of the pregnancy and provide details of the patient's participation in the study and treatment.

A pregnancy is to be reported to the sponsor within 24 hours of awareness by the study site personnel, using the Pregnancy reporting forms and contact information in Section 7.6. The expected date of delivery or expected date of the end of the pregnancy, last menstruation, estimated conception date, pregnancy result, and neonatal data, etc, should be included in this form, as available.

The investigator will follow the medical status of the mother, as well as the fetus, and will report the outcome to the sponsor.

### **7.9. Vital Signs, Physical Examinations, Clinical Laboratory Tests, Electrocardiograms, and Bone Mineral Density Measures**

Section 6.5.2 details the requirements for measurement of safety parameters including vital signs, physical examinations, clinical laboratory tests, ECGs, and bone mineral density.

### **7.10. Benefit/Risk Assessment**

Adverse drug reactions (identified risks) associated with relugolix in women include nonserious events of hot flush, headache, hyperhidrosis, and loss of bone mineral density. In this protocol, relugolix will be evaluated for its benefit on endometriosis-associated pain. Low-dose hormonal add-back therapy with estradiol and norethindrone acetate will be evaluated for maintenance of bone mineral density during treatment with relugolix.

Potential risks that may be associated with relugolix treatment in women, based on nonclinical data and data available for similar compounds, include drug interactions, cardiovascular effects (corrected QT [QTc] prolongation), hepatic enzyme increases, phospholipidosis (PLD), reproductive toxicity, and metabolic and cardiovascular changes (insulin resistance, dyslipidemia, increased weight) with an increased risk of diabetes mellitus and possible increased risk of cardiovascular disease. Additionally, there are potential risks associated with the addition of estradiol/norethindrone acetate. Summaries of findings from both nonclinical and clinical studies conducted with relugolix can be found in the current version of the Investigator Brochure.

The risk assessment and mitigation strategy for this protocol are outlined in [Table 7-2](#).

**Table 7-2 Protocol Risk Assessment and Mitigation Strategies**

Potential Risk of Clinical Significance	Mitigation Strategy	
	Impact on Eligibility	Monitoring and Withdrawal Criteria

Bone Mineral Density
 
Reversible loss of bone mineral density is a risk of the hypoestrogenic state induced by relugolix. This risk is mitigated by the co-administration of low-dose estradiol and norethindrone acetate hormonal add-back therapy.
	
Exclusion criteria for a history of osteoporosis, metabolic bone disease, and prior medical therapy for low bone mineral density was included in the parent studies.
	
Bone mineral density will be monitored at the Week 24/Baseline, Week 36, Week 52, and Week 104/Early Termination visits with specified discontinuation and follow-up criteria and all fractures will be reported as adverse events.

Drug Interactions
	
Exclusion of co-administration P-glycoprotein inhibitors/inducers.
	
Collection of adverse events.

QTc Prolongation
 
Negative Thorough QT/QTc clinical study.
	
Empiric exclusion of baseline QTcF > 470 msec in the parent studies.
	
12-lead ECG at the Week 24/Baseline and Week 52 visits, and as clinically applicable; withdrawal for QTcF > 500 msec.

Hepatic Enzymes
 
Isolated increases in hepatic transaminases have been observed in prior clinical studies. There have been no reported cases consistent with drug-induced liver injury including an increase in bilirubin. Abnormal liver test results are considered adverse events of clinical interest in this study.
	
Exclusion criteria for AST and ALT > 2 x the ULN; total bilirubin values > 1.5 x ULN
	
Abnormal liver test results (AST or ALT > 3 x ULN) that develop during the Open-Label Treatment Period will be reported within 24 hours of study personnel awareness.

Potential Risk of Clinical Significance	Mitigation Strategy	
	Impact on Eligibility	Monitoring and Withdrawal Criteria

Phospholipidosis
 
Data from nonclinical studies in rats and monkeys showed histopathological changes consistent with PLD. PLD by itself is not adverse. No clinical evidence of relugolix-related PLD-associated toxicity has been observed nor was there a clinically meaningful increase in a biomarker of PLD assessed in phase 2 clinical studies.
	
Patients with significant underlying medical conditions are excluded.
	
Routine safety monitoring including laboratory assessments, ECGs, and assessment of adverse events, including any ophthalmologic adverse events, will be monitored during this study.

Metabolic Changes
 
Metabolic changes (insulin resistance, dyslipidemia, and increased weight) with increased risk of diabetes are a potential risk of the hypoestrogenic state induced by relugolix.
	
Exclusion criteria for current medical history of cardiovascular disease in the parent studies.
	
Fasting lipids and glucose will be monitored during the study.

Reproductive Toxicity
	
Premenopausal compliance with specified acceptable non-hormonal contraception; exclusion of pregnant and lactating women.
	
Pregnancy testing at each study visit; immediate withdrawal for pregnancy.

Risk of Estradiol (1.0 mg)/Norethindrone Acetate (0.5 mg)
 
Low-dose estradiol and norethindrone acetate are approved for the prevention of postmenopausal osteoporosis and the treatment of moderate to severe vasomotor symptoms. It is contraindicated for women with a history of breast cancer or estrogen-dependent neoplasia, history of (or active) deep vein thrombosis, pulmonary embolism, thromboembolic disease (myocardial infarction or stroke within the past year), liver dysfunction, prior hypersensitivity, and pregnancy.
	
Women with breast cancer or other estrogen-dependent malignances, a history of deep vein thrombosis, pulmonary embolism, thromboembolic disease, liver dysfunction, prior hypersensitivity, migraine with aura, porphyria, and pregnancy excluded from the parent studies. Physical examination, clinical chemistries, and 12-lead ECG will be performed at the Week 24/Baseline visit.
	
Clinical chemistries assessing liver tests, fasting glucose and lipids, and urine pregnancy tests will be performed throughout the study. Adverse events will be recorded at each visit.

ALT = alanine aminotransferase; AST = aspartate aminotransferase; ECG = electrocardiogram; QTc = corrected QT interval; QTcF = QT interval by the Fridericia correction; PLD = phospholipidosis; ULN = upper limit of normal.

## **8. DATA QUALITY ASSURANCE**

### **8.1. Clinical Procedures**

Sponsor personnel or designee(s) will visit the study site, if necessary, prior to initiation of the study to review information about the study drug, protocol requirements, eCRFs, monitoring requirements, reporting of serious adverse events, and to ensure a full understanding of the Investigator Site File with the site personnel.

### **8.2. Monitoring**

This study will be monitored by the sponsor (or designee) in accordance with current Good Clinical Practice (GCP) regulations. By signing this protocol, the investigator grants permission to Myovant Sciences GmbH (or designee) and appropriate regulatory authorities to conduct on-site monitoring of all appropriate study documentation. In order to assure the accuracy of data collected in the eCRF, it is mandatory that representatives of the sponsor (or designee) have access to original source documents (eg, patient records, patient charts, and laboratory reports). During the review of these documents, the anonymity of the patient will be respected with strict adherence to professional standards of confidentiality. A study monitor will contact and visit the site regularly and will be allowed, on request at a mutually acceptable time, to inspect the various records of the study. It will be the study monitor's responsibility to inspect the eCRF at regular intervals throughout the study, to verify the adherence to the protocol and the completeness, correctness and accuracy of all eCRF entries, and to meet with the investigator to discuss study progress and compliance with the protocol and GCP. The study monitor should have access to laboratory test results and any other source records and data needed to verify the entries on the eCRF. The investigator agrees to cooperate with the study monitor to ensure that any problems detected in the course of these monitoring visits are resolved. For this study, patient data will be entered into a sponsor-approved electronic database and combined with data provided from other sources in validated datasets then transmitted electronically to the sponsor (or designee).

Management of clinical data will be performed in accordance with applicable sponsor-approved standards and data cleaning procedures to ensure the integrity of the data (eg, removing errors and inconsistencies in the data).

Adverse events and concomitant medications terms will be coded using the Medical Dictionary for Regulatory Activities (MedDRA) and the World Health Organization Drug Dictionary Enhanced (WHO-DDE), respectively.

The investigator will retain original source documents and the sponsor will receive eCRF-required data as electronic datasets. Patient initials will not be collected or transmitted to the sponsor.

## **9. STATISTICAL CONSIDERATIONS AND DATA ANALYSES**

A statistical analysis plan (SAP) will describe the detailed statistical methods and analyses for this study.

All efficacy and safety measures over the course of both the parent and extension studies will be presented by the parent study treatment group using descriptive statistics. No formal treatment comparisons will be performed for this extension study. Continuous data will be summarized by means, standard deviations, medians, maximum, minimum, and number of patients. Categorical data will be summarized by counts and percentages.

There will be two analyses: one at Week 52 and one at Week 104. A clinical study report will be generated from each analysis.

### **9.1. Randomization Methods**

This is a single-arm, open-label extension study; patients are not randomized. All patients who have entered the extension study will be treated with open-label relugolix and low-dose hormonal add-back therapy for 80 weeks.

### **9.2. Analysis Populations**

Efficacy data analyses will be performed on the modified Intent-to-Treat (mITT) Population, defined as all patients who were randomized in a parent study (MVT-601-3101 or MVT-601-3102) and who have received any amount of randomized study drug.

Safety data analyses will be performed on the Safety Population, defined as all patients who were randomized in a parent study and who have received any amount of randomized study drug.

The analysis methods for safety and efficacy endpoints are the same as those used for the parent studies, unless otherwise specified in the SAP.

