
To be assessed at Week 52
 
 
To evaluate long-term efficacy of relugolix 40 mg once daily co-administered with low-dose estradiol and norethindrone acetate for up to 52 weeks, among patients who previously completed a 24-week treatment period in one of the parent studies (MVT-601-3101 or MVT-601-3102), on endometriosis-associated pain.
 
 
To be assessed at Week 104
 
 
To evaluate long-term efficacy of relugolix 40 mg once daily co-administered with low-dose estradiol and norethindrone acetate for up to 104 weeks, among patients who previously completed a 24-week treatment period in one of the parent studies (MVT-601-3101 or MVT-601-3102), on endometriosis-associated pain.
 
	
To be assessed at Week 52
 
 
Proportion of women who respond or maintain response at Week 52/Early Termination, based on their dysmenorrhea Numerical Rating Scale (NRS) scores;
 
Proportion of women who respond or maintain response at Week 52/Early Termination, based on their NMPP NRS scores.
 
 
To be assessed at Week 104
 
 
Proportion of women who respond or maintain response at Week 104/Early Termination, based on their dysmenorrhea NRS scores;
 
Proportion of women who respond or maintain response at Week 104/Early Termination, based on their NMPP NRS scores.
 

Secondary Efficacy	

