### **9.4. Efficacy Analyses**

Unless otherwise specified, efficacy analyses will be conducted using the mITT Population.

Efficacy endpoints will be summarized by the original treatment groups assigned in the parent study.

The point estimates and 2-sided 95% confidence intervals (CI) for the primary efficacy endpoints (proportion of responders based on dysmenorrhea NRS scores and use of rescue analgesic

medications, proportion of responders based on NMPP scores and use of rescue analgesic medications) will be calculated.

A responder at a given time point and for a specific type of pain (dysmenorrhea or NMPP) is defined as a patient who had a reduction in that type of pain from Baseline in the parent study greater than or equal to a pre-determined threshold and who did not have an increase in the use of rescue analgesic medications for endometriosis-associated pain compared with the use at Baseline. Patients who had a pain reduction less than the pre-determined threshold or who had an increase in the use of analgesics for endometriosis-associated pain will be considered non-responders. The pain reduction thresholds will be determined for NMPP and dysmenorrhea separately (see the SAP for details) for the parent studies and these same thresholds will be applied to this study.

Baseline values are calculated using the Baseline pain assessment period, which is defined as the period from the date of the first dose of placebo in the parent study Run-In Period through the day prior to the first dose of randomized study drug. Patients' average NRS pain scores and use of rescue analgesic medications for endometriosis-associated pain (dysmenorrhea or NMPP) will be compared between a given visit-specific pain assessment period (eg, Week 28, Week 32, etc.) and the Baseline pain assessment period. The visit-specific pain assessment period is defined as the last 35 calendar days immediately prior to and including the last dose of study drug treatment received prior to the visit date.

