	
Baseline and the end of the extension study (Week 104) for the following parent study treatment groups:
 
 
• Parent Study Group A: Randomized to 24 weeks of oral relugolix 40 mg once daily co-administered with 1.0 mg estradiol and 0.5 mg norethindrone acetate in the parent study;
 
• Parent Study Group B: Randomized to 12 weeks of oral relugolix 40 mg once daily followed by 12 weeks of oral relugolix 40 mg once daily co-administered with 1.0 mg estradiol and 0.5 mg norethindrone acetate in the parent study;
 
• Parent Study Group C: Randomized to placebo in the parent study.
 
 
The parent study Baseline will be used as the reference point for this extension study for all change from baseline-related endpoints. The pain scores during the Baseline Pain Assessment Period of the parent study will establish the patient's baseline for both the parent study and the extension study.
 
Primary Efficacy Endpoints
 
Week 52
 
 
• Proportion of women who respond or maintain response at Week 52/Early Termination, based on their dysmenorrhea NRS scores;
 
• Proportion of women who respond or maintain response at Week 52/Early Termination, based on their NMPP NRS scores.
 
 
Week 104
 
 
• Proportion of women who respond or maintain response at Week 104/Early Termination, based on their dysmenorrhea NRS scores;
 
• Proportion of women who respond or maintain response at Week 104/Early Termination, based on their NMPP NRS scores.
 
 
Secondary Efficacy Endpoints
 
To be assessed at Week 52 and Week 104, unless otherwise specified
 
 
• Change from the parent study Baseline in the EHP-30 Pain Domain scores;
 
• Change from the parent study Baseline in the mean dysmenorrhea NRS score;
 
• Proportion of patients who are better or much better on the PGIC for dysmenorrhea (at Week 52 only);
 
• Change from the parent study Baseline in the mean NMPP NRS score;
 
• Change from the parent Baseline in the mean NRS score;
 
• Proportion of patients not using opioids;
 
• Proportion of patients not using analgesics;
 
• Proportion of patients who are better or much better on the PGIC for NMPP (at Week 52 only);
 
• Change from the parent study Baseline in the mean dyspareunia NRS scores;
 
• Proportion of patients who are better or much better on the PGIC for dyspareunia (at Week 52 only);
 

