#### Efficacy

Efficacy data will be summarized by the original randomized treatment group assigned in the parent study (ie, Parent Study Groups A, B, and C) for the modified Intent-to-Treat Population. The analyses methods for efficacy endpoints are similar to those used for the parent studies, unless otherwise specified in the statistical analysis plan (SAP).

The point estimate and 2-sided 95% confidence interval (CI) for the primary efficacy endpoints (proportion of responders based on dysmenorrhea NRS scores and use of rescue analgesic medications, proportion of responders based on NMPP scores and use of rescue analgesic medications) will be calculated.

The methods for analyzing the additional efficacy endpoints are described in the SAP.

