### Sample Size Estimation

Because this is an extension study, the sample size will be determined by the number of patients who have completed a parent study (MVT-601-3101 or MVT-601-3102) and who are eligible and willing to participate in the extension study. It is estimated that approximately 800 patients (67% of the total of 1200 patients who will be randomized into the parent studies) will participate in this study.

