
To be assessed at Week 52
 
 
To evaluate long-term efficacy of relugolix 40 mg once daily co-administered with low-dose estradiol and norethindrone acetate for up to 52 weeks, among patients who previously completed a 24-week treatment period in one of the parent studies (MVT-601-3101 or MVT-601-3102), on endometriosis-associated pain.
 
 
To be assessed at Week 104
 
 
To evaluate long-term efficacy of relugolix 40 mg once daily co-administered with low-dose estradiol and norethindrone acetate for up to 104 weeks, among patients who previously completed a 24-week treatment period in one of the parent studies (MVT-601-3101 or MVT-601-3102), on endometriosis-associated pain.
 
	
To be assessed at Week 52
 
 
Proportion of women who respond or maintain response at Week 52/Early Termination, based on their dysmenorrhea Numerical Rating Scale (NRS) scores;
 
Proportion of women who respond or maintain response at Week 52/Early Termination, based on their NMPP NRS scores.
 
 
To be assessed at Week 104
 
 
Proportion of women who respond or maintain response at Week 104/Early Termination, based on their dysmenorrhea NRS scores;
 
Proportion of women who respond or maintain response at Week 104/Early Termination, based on their NMPP NRS scores.
 

Secondary Efficacy	

To be assessed at Week 52 and Week 104
 
To evaluate long-term efficacy of relugolix 40 mg once daily co-administered with low-dose estradiol and norethindrone acetate, among patients who previously completed a 24-week treatment period in one of the parent studies (MVT-601-3101 or MVT-601-3102), on the following:
 
 
Function, as measured by the Endometriosis Health Profile (EHP)-30 Pain Domain;
 
Dysmenorrhea, as measured by the NRS for dysmenorrhea;
 
Patient Global Impression of Change (PGIC) for dysmenorrhea;
 
	
To be assessed at Week 52 and Week 104, unless otherwise specified
 
 
Change from the parent study Baseline in the EHP-30 Pain Domain scores;
 
Change from the parent study Baseline in the mean dysmenorrhea NRS score;
 
Proportion of patients who are better or much better on the PGIC for dysmenorrhea (at Week 52 only);
 

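### The default population for the Week 52 and Week 104 primary responder proportions includes about 400 women who are not expected to enter the extension and so can have no result at those visits

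*Protocol*

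**What the plan says.** **Population.** Protocol Section 9.2 reads: "Efficacy data analyses will be performed on the modified Intent-to-Treat (mITT) Population, defined as all patients who were randomized in a parent study". The only other condition is having taken some randomized study drug. Neither completing 24 weeks nor entering the extension is required. Section 9.4 adds: "Unless otherwise specified, efficacy analyses will be conducted using the mITT Population". The synopsis, under Efficacy, states: "Efficacy data will be summarized by the original randomized treatment group assigned in the parent study (ie, Parent Study Groups A, B, and C"), and names the modified Intent-to-Treat Population for this summary.

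**Objective and endpoints.** Section 3 limits the primary objective to effects "among patients who previously completed a 24-week treatment period in one of the parent studies (MVT-601-3101 or MVT-601-3102), on endometriosis-associated pain". The matching endpoints are proportions such as "Proportion of women who respond or maintain response at Week 52/Early Termination, based on their NMPP NRS scores" and, for the later time point, "Proportion of women who respond or maintain response at Week 104/Early Termination, based on their dysmenorrhea NRS scores".

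**Who enters.** Inclusion criterion 1 requires completion of 24 weeks in a parent study. Section 4.1 defines enrollment by the first dose of MVT-601-3103 drug. The sample size statement (synopsis and Section 9.3) expects that "approximately 800 patients (67% of the total of 1200 patients who will be randomized into the parent studies) will participate in this study".

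**Version.** The document contains Amendment 2 in full and the first part of a later version, which breaks off in Section 6.5.2.6. Section 9.2 can be read only in the Amendment 2 text. The later synopsis still names the mITT Population for efficacy but does not define it.

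**The concern.** The objective asks how women who completed a parent study fare on up to 52 or 104 weeks of relugolix with add-back. The population set for the answer is everyone dosed in a parent study. Those who do not enter take no extension drug and attend no extension visit. In Group C, non-entrants took placebo only and never received relugolix.

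The efficacy analysis has no hypothesis test, so the point estimate and its 95% confidence interval are the whole primary result, and they go into two clinical study reports. With a denominator that does not match the objective, a reader cannot tell whether the proportion describes response on continued treatment, response combined with entry into the extension, or a mixture of results from different treatment durations.

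The protocol does state the restriction elsewhere. In the synopsis, the Week 52 lumbar-spine bone density comparison is limited to Group A women who enrolled in the extension. The primary efficacy proportions carry no such limit.

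**Working it through.** **Inputs from the protocol**
- Randomized in the parent studies: 1,200 (Section 9.3). This is an upper limit for the mITT, which also requires dosing.
- Expected to enter the extension: about 800 (Section 9.3).
- Response rates, allocation ratio and entry by group: not given. The values below are assumptions, shown over a range.

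**The protocol's own figure**
- 800 / 1,200 = 66.7%, which agrees with the stated 67% (0.67 × 1,200 = 804).
- Non-entrants: 1,200 − 800 = 400, and 400 / 1,200 = 33.3% of the stated denominator.

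**Three ways the SAP might treat the non-entrants**

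1. *Non-responders.* Reported proportion = p × 800 / 1,200, where p is the response rate among entrants. It cannot exceed 66.7%.

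| Assumed p among entrants | Reported over 1,200 |
|---|---|
| 60% | 40.0% |
| 70% | 46.7% |
| 80% | 53.3% |
| 90% | 60.0% |

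 With 95% Wilson intervals at p = 80%: 640/800 = 80.0% (77.1 to 82.6) against 640/1,200 = 53.3% (50.5 to 56.1). The results will be reported by parent group. Assuming equal allocation and equal entry (267 of 400 per group), the same comparison is 214/267 = 80.1% (75.0 to 84.5) against 214/400 = 53.5% (48.6 to 58.3). The shift is far larger than the sampling error.

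2. *Last parent-study status carried forward.* Reported proportion = (p × 800 + q × 400) / 1,200, where q is the response rate assumed for non-entrants. At p = 80%:
 - q = 20%: (640 + 80) / 1,200 = 60.0%
 - q = 40%: (640 + 160) / 1,200 = 66.7%
 - q = 60%: (640 + 240) / 1,200 = 73.3%

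 A third of the results labelled Week 52 or Week 104 would then come from at most 24 weeks of treatment, and from placebo alone in Group C.

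3. *Observed cases only.* The denominator falls to roughly the enrolled women and the estimate stays near p. This comes closest to the objective, but it is not an analysis of the population that Section 9.2 defines.

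**Three different sets.** The objective names 24-week completers (number not given), the extension treats completers who are also eligible and willing (about 800), and the mITT is everyone dosed (at most about 1,200). The text does not say which of these the primary proportions describe.

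**The case against.** There is a fair case that the mismatch does less harm than it seems.

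- *The handling is not yet fixed.* Section 9.4 leaves missing data to the SAP, and Sections 9.2 and 9.4 both allow exceptions. A reader might infer that the 400 or so non-entrants must be counted as non-responders or carried forward, so that the primary estimate is bound to be distorted. The protocol does not support that. Section 9.4 describes a non-responder by an insufficient pain reduction or an increase in analgesic use, both of which need data. Its pain window is tied to a visit date, and Section 6.3 reserves Early Termination for women leaving this study. Nothing turns a parent-study window into a Week 52 or Week 104 result. This stands: the size of the effect is conditional.
- *A whole-cohort display may be intended.* Section 9 says measures across both the parent and extension studies will be shown by parent group, and keeping all randomized women limits selection on completing and continuing. This supports keeping the mITT as a supportive analysis. It does not make women who took no extension drug informative about long-term treatment.
- *Nothing is decided on the figure.* There are no formal treatment comparisons and there is no efficacy margin. The one threshold rule, for bone density at Week 52, already carries the enrollment limit in the synopsis. This stands and lowers the severity.
- *The current Section 9.2 cannot be seen.* The defect is shown for Amendment 2 and only inferred for the later version, whose synopsis still names the same population.

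**Conclusion.** The point holds as a mismatch between a stated population and a stated objective. About one third of the default denominator (400 of 1,200, taking 1,200 as an upper limit and 800 as an estimate) can have no Week 52, Week 104 or extension Early Termination result. No missing-data rule makes that denominator fit the objective, because each either adds values for women outside the extension or quietly drops them from the defined set.

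The numerical consequence is not established. It runs from almost none (observed cases) to multiplication of the entrant response rate by 0.667 (non-responder counting), and every response rate used above is assumed. It would go too far to say that the primary results will be understated by a known amount. This should be fixed but is not critical, because the efficacy analysis is descriptive and no success criterion rests on it.

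**What to change.** In Sections 9.2 and 9.4 and in the synopsis, define the population for the Week 52 and Week 104 primary proportions as women randomized in a parent study who received at least one dose of MVT-601-3103 study drug, summarized by Parent Groups A, B and C. This uses the protocol's own definition of enrollment and matches the limit that the synopsis already sets for Group A in the Week 52 bone density analysis. Keep the parent mITT for the whole-course presentation in Section 9, labelled as supportive, with an explicit rule for women who did not enter. Check that Section 9.2 of the later version and the SAP carry the same definition.

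The cost is one definition and its cross-references, with no change to data collection. The drawback is that the enrolled set is selected on completing 24 weeks, being eligible and choosing to continue. This should be stated beside the results, with the number of non-entrants in each parent group.
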